Strategies used to improve adherence to intervention protocols included weekly phone calls with participants to report previous week's specific food intake, report current body weight, and troubleshooting/support from a Registered Dietitian. Procedures for monitoring adherence include the measurement of respiratory quotient by indirect calorimetry, body weight and composition by bioelectrical Impedance Analysis and blood draw for the quantification of β -hydroxybutyrate, insulin, glucose, triglycerides, and cholesterol.

11d Interventions: concomitant care

Participants will be prohibited from participating in other weight loss programs (diet, exercise, and/or medications that induce weight loss). Participants will be instructed to continue their usual physical activity while in the study.

12. Outcomes

Main outcome measures: S_1 and AIR_g will be measured at baseline with an intravenous glucose tolerance test, body composition with bioimpedance at baseline and Wk10. REE and body composition will also be measured at week 5. REE, TEE, and mechanical efficiency (ME) will be measured with indirect calorimetry, doubly labeled water, and a submaximal bike test, respectively, at baseline and Wk14.

13. Participant timeline

Participants were enrolled between June 2019 and August 2023. Participants will complete 10 weeks of hypocaloric diet, 4 weeks of weight stabilization, and 6 months of weight loss maintenance. See figure 1.

[figure not shown]

Fig. 1 Schematic diagram of the study design.

14. Sample size

This study was powered for differences in FM loss between the two diet groups. Our published data indicate that AA (both men and women) lose more FM when consuming a LG vs HG diet over 16 weeks (1). Subgroup analysis within only the AA women (n=17), for only the 8-week hypocaloric phase, indicated that the women lost more FM with the LG diet [4.5 ± 1.0 (SEM) kg] vs the HG diet [2.0 ± 0.9 (SEM) kg] at a significance level of $P=0.113$. Based on these numbers, with 74 women (37/ group) we would have 80% power to detect a difference of 2.5 kg in FM loss between diets.

15. Recruitment

We will recruit from the local communities (UAB, city of Birmingham, and Jefferson and Shelby counties) via radio, newspaper, web-based advertisement, television advertisement, Research Match, UAB Reporter, word of mouth, and posting of flyers.

Methods: Assignment of interventions

16a Allocation: sequence generation

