All records pertaining to medical history, participation in this study, and data collected will be kept strictly confidential and will be recorded only by study number, to protect participant privacy. Only study investigators and the UAB IRB will have access to this data. Information regarding participant demographics, body composition, metabolic outcomes, or blood outcome measures will be shared and labeled with the study number, a unique identifier, and the date of acquisition.

20a Statistics: outcomes

Statistical analysis will be performed with SPSS version 29 (SPSS Inc., Chicago, IL), and data presented as mean \pm SD (or SEM). Statistical significance will be set at $P < 0.05$, unless otherwise specified, and normality of variables was assessed by visual inspection of histogram and Shapiro-Wilk test. Participants will be included in the analysis if they have S_I data at baseline, and body composition at baseline and week 10.

To test the hypothesis that AA women with obesity randomized to a low-CHO diet lose more FM than those randomized to a low-fat diet, we will analyze data from Phase 1 with generalized linear models (GLM). FM at week 10 will be the dependent variable, baseline FM, diet group, and S_I (and/or AIR) the covariates. Finally, to test the hypothesis that S_I (and/or) modulates the response to diet, a “diet \times S_I ” interaction term will be added to the models; i.e., $\Delta FM = \beta_0 + \beta_1 \text{ baseline FM} + \beta_2 \text{ baseline } S_I + \beta_3 \text{ diet group} + \beta_4 \text{ diet group} * S_I + e_1$.

To test the hypothesis that AA women with obesity randomized to a low-CHO diet maintain a higher TEE and REE, and a lower ME, than those randomized to a low-fat diet, we analyzed data from the end of Phase 2 with GLM. TEE, REE, or ME (week 14) were the dependent variables; baseline TEE, REE, or ME, diet group, and S_I (and/or AIRg) the covariates. For all

outcomes, we tested for a phenotype-by-diet interaction by adding relevant interaction terms to the model; e.g., $\Delta\text{TEE} (\text{week 14} - \text{baseline}) = \beta_0 + \beta_1 \text{baseline TEE} + \beta_2 \text{baseline S}_i + \beta_3 \text{diet group} + \beta_4 \text{diet group} * \text{S}_i + e_1$.

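### The 80% power stated for 37 women per group does not follow from the pilot figures cited for it, which give about 92–97% with complete data

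*Combined protocol and SAP*

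**What the plan says.** Section 14 (Sample size) names the comparison that was powered: "This study was powered for differences in FM loss between the two diet groups". Its inputs come from a subgroup of 17 African American women over an 8-week hypocaloric phase: "the women lost more FM with the LG diet [4.5 ± 1.0 (SEM) kg] vs the HG diet [2.0 ± 0.9 (SEM) kg", with P=0.113. It then concludes: "Based on these numbers, with 74 women (37/ group) we would have 80% power to detect a difference of 2.5 kg".

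Section 14 gives no SD, pilot arm sizes, test, alpha, sidedness or allowance for losses, and does not say whether 74 is the number randomised or the number evaluable. Section 20a supplies the alpha: "Statistical significance will be set at $P < 0.05$, unless otherwise specified". It also restricts the analysis set: "Participants will be included in the analysis if they have S_I data at baseline, and body composition at baseline and week 10". Section 20c, on the analysis population and missing data, is marked N/A. Section 8 sets 1:1 allocation.

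**The concern.** The sentence presents 80% as derived from the pilot figures just before it, so it can be checked. A pilot of 17 women with SEMs near 1 kg implies an SD a little under 3 kg. A 2.5 kg difference is then most of one SD, for which 37 per group is generous.

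What is at stake is how the result is read. If the printed SEMs are the basis, 37 per group leaves a wide margin for women without baseline S_I or week-10 body composition. If an unstated SD near 3.8 kg was used with complete data, there is no margin, and any exclusion takes power below 80%. A null result with incomplete follow-up means something different in each case, and the text does not say which applies.

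**Working it through.** **Inputs from the documents.** Difference 2.5 kg; 37 per group; SEMs 1.0 (LG) and 0.9 (HG); 17 pilot women in total (section 14). Alpha 0.05 (section 20a).

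**Assumptions, because the documents are silent.** Raw SEMs; a two-sided t-test with a pooled SD; a pilot split (LG/HG) from 5/12 to 12/5; all 37 per group evaluable. The planned adjustment for baseline fat mass is not credited.

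**1. What the plan's own figure requires.** Power is taken from the noncentral t with 72 df and noncentrality 2.5 / (SD × √(2/37)). Setting it to 80% gives SD = 3.79 kg. The normal approximation gives 2.5 / (2.802 × √(2/37)) = 3.84 kg.

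**2. What the pilot figures imply.** SD per arm = SEM × √n. Pooled SD = √{[(n₁−1)·n₁·SEM₁² + (n₂−1)·n₂·SEM₂²] / 15}.

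- Split 8/9: √[(7×8×1.00 + 8×9×0.81)/15] = √(114.32/15) = 2.76 kg. Noncentrality 2.5/(2.76×0.2325) = 3.90; power 97.0%.
- Split 12/5: √[(11×12×1.00 + 4×5×0.81)/15] = √(148.2/15) = 3.14 kg. Noncentrality 2.5/(3.14×0.2325) = 3.42; power 92.1%.

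| Split LG/HG | Pooled SD (kg) | Power at 37/group | n/group for 80% | Difference detectable at 80% (kg) |
|---|---|---|---|---|
| 5/12 | 2.91 | 95.4% | 23 | 1.92 |
| 6/11 | 2.82 | 96.4% | 21 | 1.86 |
| 7/10 | 2.77 | 96.9% | 21 | 1.83 |
| 8/9 | 2.76 | 97.0% | 21 | 1.82 |
| 9/8 | 2.80 | 96.7% | 21 | 1.85 |
| 10/7 | 2.88 | 95.8% | 22 | 1.90 |
| 11/6 | 2.99 | 94.4% | 24 | 1.98 |
| 12/5 | 3.14 | 92.1% | 26 | 2.08 |

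The SD needed for 80% exceeds the implied SD by 21% (3.79/3.14) to 37% (3.79/2.76). Simulation of 200,000 trials at 37 per group agrees: 97.0% at SD 2.76, 92.1% at 3.14 and 80.0% at 3.79.

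**3. Sensitivity to the assumptions.**

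- Rounding: SEMs from 0.95/0.85 to 1.05/0.95 give SD 2.61–3.30 kg, power 89–98%, and 19–29 per group for 80%.
- Extreme splits, pooled SD: 13/4 gives 89.1%, 14/3 gives 85.2%, and 15/2 gives 80.6%.
- Arm-specific SDs with an unequal-variance test: 97.7% at 2/15 falling to 95.4% at 15/2. With both SEMs at the upper rounding limit, 96.4% falling to 93.5%.
- Cross-check from P=0.113, if it came from an ordinary t-test on 15 df: t = 1.683, SE of the difference 2.5/1.683 = 1.49 kg, and SD at most 3.06 kg (at 8/9 or 9/8). Power is then at least about 93.5%. The conclusion does not depend on this, because the pilot test is not named, and I claim no error in that P value.
- One-sided testing raises power further.

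**4. Could losses explain it?** To bring power down to 80%, the loss would have to be 1 − 26/37 = 30% to 1 − 21/37 = 43%. A loss of about 20% (30 per group) still leaves 86–93%. By contrast, with SD 3.79 kg and 30 per group the noncentrality is 2.5/(3.79×√(2/30)) = 2.55 and power about 71%.

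**The case against.** The strongest reply is that the paragraph is under-specified rather than shown to be wrong. Every replacement figure rests on assumptions about the split, the test and the SEMs, and several unstated inputs would bring 80% within reach:

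- **Alpha of 0.01.** With an SD of about 3.05 kg this gives about 81%, but it conflicts with the 0.05 in section 20a, and section 14 specifies nothing different.
- **Reading 17 as the size of each pilot arm.** This gives an SD of 3.7–4.1 kg and power of 73–82%. It is a plausible slip, but it contradicts the text, where 17 is the subgroup total.
- **Planning on the larger SD of the two arms.** This gives 86.5% at 12/5, or 83.1% with the SEM at 1.05. It comes near 80% only at splits as uneven as 14/3.
- **Model-adjusted SEMs, or a deliberately inflated SD.** Inflation would be defensible: with 15 df and an SD of 2.76 kg, the upper 95% confidence limit is about 4.3 kg. But the paragraph mentions neither.

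These possibilities explain how 80% may have arisen, but they do not make it follow from the figures named as its basis. Two parts of the objection stand. The 92–97% range is conditional and should not be printed as if it were firm. The consequences are also limited: the discrepancy is conservative, and section 13 reports enrolment as running from June 2019 to August 2023, so correcting the text will not alter recruitment.

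**Conclusion.** The concern holds. The stated power is wrong as derived: the cited pilot figures give 92–97% at 37 evaluable per group, or 89–98% allowing for rounding of the SEMs, against the stated 80%. This rests on raw SEMs, a pooled SD, a two-sided 5% t-test, and a pilot split no more uneven than 5/12 or 12/5. With arm-specific SDs it is 95–98% at any split from 2/15 to 15/2. Nothing elsewhere in the document supplies the larger SD, stricter alpha or loss allowance needed to restore 80%. This is a defect in a relied-upon figure and its derivation, not a shortage of participants. It concerns the diet main effect only; power for the diet-by-S_I interaction was not examined here.

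**What to change.** Rewrite the last sentence of section 14 with the inputs actually used, for example: *Assuming an SD of [value] kg (pilot arms n=[a] and n=[b]), a two-sided alpha of 0.05 and [test], [n] evaluable women per group give [x]% power for a difference of 2.5 kg.*

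- If the printed SEMs are the basis and all 37 per group are taken as evaluable, replace 80% with the value for the true pilot split, or state 80% power for the corresponding smaller difference (about 1.8–2.1 kg over the splits considered).
- If a larger SD, a different alpha or an allowance for losses led to 37, state it and the reason.
- In either case, say whether 74 is randomised or evaluable, and give the evaluable number per group, under the section 20a inclusion rule, at which 80% holds.

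The cost is one reworded paragraph. It needs no more participants and no design change.

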Energy requirements will be estimated by multiplying REE, measured with indirect calorimetry, by 1.5 (PA factor), and all participants will receive an individualized dietary prescription throughout the weight loss phase (60% of estimated energy needs or 40% energy deficit) and during the 4-week weight stabilization period (energy balance (EB)). During the weight stable phase, diets will be adjusted if weight is not stable. All the food for the duration of Phases 1 and 2 was delivered to the participants' homes on a weekly basis. The low-fat diet was aligned with the USDA guidelines (<http://health.gov/dietaryguidelines/2015/guidelines/>), and was comprised of 55% CHO, 20% fat, and 25% protein. The low-CHO diet was comprised of 25% CHO, 55% fat and 25% protein. Both diets emphasized complex over simple CHO, and allowed dairy products, fruits, and vegetables, within the CHO allowance of each diet.

This will be followed by a 6-month weight maintenance phase with dietary prescription only, where participants will provide their own food. There will be monthly peer group support meetings with the dietitian to discuss nutrition education topics (such as food label reading, portion sizes, tips on eating out, etc). Participants will individually report their body weight to the dietitian and turn in an 8-day food record every month for 6 months.

11b Interventions: modifications

On 06/17/2020, the protocol was amended and approved by UAB IRB to minimize in person contact with participants due to COVID. DXA was replaced with an at home creatine dilution test to measure muscle mass. The post intervention (week 14) IVGTT and Mixed Meal Tolerance tests were omitted from the protocol. The Oral Glucose Tolerance Test at screening was replaced with measurement of Hemoglobin A1c finger stick (choice of at home or in person). Food was delivered to participants home via a commercial provider. The REE and Exercise tests were optional, if participants were not comfortable completing these in-person visits. Participants were given the option to complete the TEE visit at home or in-person. The weekly in-person meetings with the dietitian were moved to a Zoom or phone call and the monthly peer group meetings in Phase 3 were moved to Zoom. Food records were emailed and/or discussed via phone call, with food intake and body weight reported.

11c Interventions: adherance

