Resting Energy Expenditure and substrate utilization will be determined in the CCTS/NORC/DRC Core Laboratory by indirect calorimetry (TrueOne 2400, Parvo Medics, Sandy, UT). Participants will be tested in the fasted (10h) condition following a 30-min supine rest at baseline and week 14.

Total Energy Expenditure will be measured through the CCTS/NORC/DRC Core Laboratory by doubly-labeled water (DLW), at baseline and week 14, using a protocol based on established procedures (3). A FQ of 0.85 will be used at baseline to reflect a standard omnivorous diet, while at week 14, the FQ of the intervention diets will be used (4). FQ will be calculated using the equation of Black et al, $FQ = (CHO\% \times 1.00) + (fat\% \times 0.71) + (protein\% \times 0.81)$ (4).

Mechanical efficiency will be assessed using a submaximal cycling test, in the fasted state, at baseline and week 14. Following a familiarization period, participants cycled at 60 RPM at 10, 20 and 50 watts of power in 4-minute increments. Ventilation, oxygen uptake, carbon dioxide production, respiratory exchange ratio, and heart rate were obtained throughout. Net skeletal muscle work efficiency will be expressed as the ratio of power generated (kcal/min) to the change in EE above REE (kcal/min) at each power output (5).

Laboratory analyses. Blood samples will be collected in the fasting state and concentrations of glucose, β HB, total cholesterol, HDL-cholesterol and triglycerides measured using a SIRRUS analyzer (Stanbio, Boerne, TX), and insulin using a TOSOH A1A-900 immunoassay analyzer (TOSOH Bioscience, South San Francisco, CA) in the CCTS/DRC Core Laboratory. LDL-cholesterol will be calculated using the Friedewald formula (6).

18b Data collection plan: retention

Participant retention will be promoted by weekly communications from the study dietitians and reminder communications from the study coordinators for upcoming in-person testing visits.

19. Data management

Confidentiality will be maintained by coding all data with the subject's identification number. Computerized data will be stored in the Department of Nutrition Sciences database. Paper data will be stored in the Department of Nutrition Sciences in a locked room in a file cabinet. Only qualified research personnel will have access to the database containing the subject information. All subject data that are entered into statistical analyses and publication reports will refer to individuals only by number rather than name.

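### Week-14 TEE uses an arm-specific diet FQ, so drift of both arms toward a common diet would inflate the low-CHO minus low-fat difference, and no sensitivity analysis is planned

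*Combined protocol and SAP*

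**What the plan says.** Section 18a (Total Energy Expenditure) sets the FQ by time point. For baseline: "A FQ of 0.85 will be used at baseline to reflect a standard omnivorous diet". For follow-up: "at week 14, the FQ of the intervention diets will be used". The FQ comes from an equation in the percentages of carbohydrate, fat and protein, so I read the week-14 value as one number per assigned diet.

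Section 11a gives the compositions. The low-fat diet "was comprised of 55% CHO, 20% fat, and 25% protein", which totals 100%. For the other arm: "The low-CHO diet was comprised of 25% CHO, 55% fat and 25% protein", which totals 105%. Section 11a also says that all food was supplied during the weight-loss and stabilization phases, that is, up to week 14.

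Section 20a states the hypothesis that low-CHO women "maintain a higher TEE and REE, and a lower ME, than those randomized to a low-fat diet". It is tested with week-14 TEE as the dependent variable and baseline TEE, diet group and S_I and/or AIRg as covariates.

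Section 11c lists adherence checks, including "measurement of respiratory quotient by indirect calorimetry", beta-hydroxybutyrate and weekly reports of food intake. Nothing links these to the FQ used for TEE. Sections 20b and 20c are entered as N/A.

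**The concern.** Doubly labelled water measures CO2 production, and the FQ turns it into energy. A lower FQ gives more energy per litre of CO2. Because the week-14 FQ is set by diet arm, two women with identical CO2 production get different TEE values according to their assignment, and the low-CHO value is the higher one. That is right if each woman eats the macronutrient mix of her assigned diet. If the arms drift toward each other, part of the difference is produced by the conversion factor, and it lies in the direction of the hypothesis.

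Baseline adjustment does not help, because baseline TEE uses the same FQ in both arms. Without a planned check, a reader of the results could not tell a metabolic effect from a conversion effect. TEE is a secondary outcome, so the fat-mass analysis is not affected.

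**Working it through.** The plan states no diet FQ, TEE effect or TEE standard deviation, so there is no figure to reproduce.

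**Assumptions not in the documents**
- Conversion: E(FQ) = 1.106 + 3.941/FQ kcal per litre of CO2 (Weir type). Two close variants change the between-diet ratio by at most about 0.5 percentage points.
- True TEE: 2,200 kcal/day in both arms. All results scale in proportion, so 2,000 multiplies them by 0.91 and 2,800 by 1.27.
- Drift target: FQ 0.85, the protocol's own baseline value.

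**Step 1: diet FQs** from the section 18a equation, FQ = 1.00 × CHO + 0.71 × fat + 0.81 × protein.
- Low-fat 55/20/25: 0.5500 + 0.1420 + 0.2025 = 0.8945.
- Low-CHO as printed, 25/55/25: 0.2500 + 0.3905 + 0.2025 = 0.8430, with a total of 105%.
- Low-CHO brought to 100% (illustrations only, none endorsed): 25/50/25 gives 0.8075; 25/55/20 gives 0.8025; 20/55/25 gives 0.7930; rescaling gives 0.843/1.05 = 0.8029. The range is 0.793-0.8075.

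**Step 2: effect of the FQ at equal CO2 production.** E(0.8945) = 5.5118, E(0.85) = 5.7425, E(0.843) = 5.7810, E(0.8075) = 5.9865, E(0.793) = 6.0757.
- Printed: 5.7810/5.5118 = 1.049, so low-CHO TEE is 4.9% higher.
- At 100%: 5.9865/5.5118 = 1.086 to 6.0757/5.5118 = 1.102, so 8.6-10.2% higher.

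**Step 3: bias under drift.** FQ eaten = FQ assigned + d × (0.85 − FQ assigned). Bias per arm = 2,200 × [E(assigned)/E(eaten) − 1].

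Half drift (d = 0.5):
- Low-fat eats 0.87225: 2,200 × (5.5118/5.6242 − 1) = −44.
- Low-CHO printed eats 0.8465: 2,200 × (5.7810/5.7616 − 1) = +7.
- Low-CHO 25/50/25 eats 0.82875: 2,200 × (5.9865/5.8614 − 1) = +47.
- Low-CHO 20/55/25 eats 0.8215: 2,200 × (6.0757/5.9033 − 1) = +64.

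Spurious low-CHO minus low-fat difference, kcal/day (from unrounded values):

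| Drift of both arms toward 0.85 | Printed (0.843) | 25/50/25 (0.8075) | 20/55/25 (0.793) |
|---|---|---|---|
| 25% | +26 | +45 | +54 |
| 50% | +51 | +91 | +108 |
| 100% | +103 | +182 | +216 |

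**Step 4: other departures**, with low-CHO FQ 0.8025 (E = 6.0169) as one illustration.
- Low-CHO women eat 10 points less CHO and 10 more fat (FQ 0.7735, E = 6.2010): 2,200 × (6.0169/6.2010 − 1) = −65, so the difference moves by −65.
- Low-fat women eat 10 points more CHO and 10 less fat (FQ 0.9235, E = 5.3735): 2,200 × (5.5118/5.3735 − 1) = +57, so the difference moves by −57.
- Both arms shift 10 points from CHO to fat: about −8. Both shift from fat to CHO: about +8.
- Wrong amount with an unchanged mix: 0 through the FQ.

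**Step 5: the 105% total.** Energy shares actually eaten cannot exceed 100%. If 0.843 is applied while adherent women eat a diet with FQ 0.793-0.8075:
- 2,200 × (5.7810/5.9865 − 1) = −76.
- 2,200 × (5.7810/6.0757 − 1) = −107.

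On this reading the net between-arm bias runs against the hypothesis at low drift and is about −2 to +14 kcal/day at half drift. The printed column in Step 3 holds only if 0.843 is the true FQ of the diet supplied.

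**The case against.** The strongest reply is that all food is provided through week 14. The FQ of supplied food is then an estimate of intake based on known composition, and not a bare assignment label. If women eat what they are sent, the diet FQ is the right one and a common FQ is wrong. With a common 0.85 and full adherence, low-fat TEE is overstated by 2,200 × (5.7425/5.5118 − 1) = 92. Low-CHO TEE is understated by 90 (25/50/25: 5.7425/5.9865) to 121 (20/55/25: 5.7425/6.0757). The difference is therefore too small by about 182-213 kcal/day. This stands, and it is why the diet-FQ analysis should stay. It does not remove the point: the food is eaten at home, the plan itself monitors adherence, and it says nothing about what happens to TEE if that monitoring shows departures.

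The second reply is that the proposed checks are weak. Intake up to week 14 is self-reported by phone, and the documents do not say that macronutrients are derived from it; the 8-day food records in section 11a belong to the maintenance phase. RQ is a fasting measurement and may be incomplete, because section 11b made REE tests optional. This also stands. It argues against making the TEE claim depend on reported intake, but not against showing the result under more than one FQ.

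A reader might infer that any non-adherence favours low-CHO. The documents do not support that: Step 4 shows departures that cancel or reverse the sign, and eating too much or too little of the right mix has no effect through the FQ.

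**Conclusion.** The point holds as a conditional one. The conversion factor differs by arm at week 14, baseline adjustment cannot correct it, and no sensitivity analysis is planned. Convergence of the arms toward a common or habitual diet would inflate the low-CHO minus low-fat TEE difference. At half drift the size is about 51 kcal/day (printed macronutrients) or 91-108 kcal/day (totals of 100%); at full drift it is about 103 or 182-216 kcal/day. These figures rest on the assumed conversion, TEE level and drift target. The documents give no adherence rate, and food provision makes large drift less likely.

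A reader might also take the full 4.9% or 8.6-10.2% gap at equal CO2 production (about 107 or 189-225 kcal/day at 2,200) as bias. It is not: it is a real energy difference if the assigned diets are eaten, and becomes wholly artefact only if both arms eat the same mix.

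The 105% total leaves the low-CHO FQ undefined. Depending on how it is resolved, the error could run against the hypothesis, so neither sign nor size can be settled until section 11a is reconciled.

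**What to change.** 1. Reconcile the low-CHO percentages in section 11a before any FQ is calculated, and state in section 18a the FQ used for each diet.
2. Keep the diet-FQ analysis of week-14 TEE. Add to section 20b a sensitivity analysis with one common FQ in both arms, and another with an individual FQ from reported intake where macronutrients can be derived.
3. Show these with fasting RQ and beta-hydroxybutyrate by arm, and report how much of the between-arm difference comes from the FQ choice.
4. Describe a TEE advantage that appears only under the diet FQ as dependent on that assumption.

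The common-FQ recalculation uses CO2 production already measured and needs no new visits. The individual-FQ analysis depends on whether the intake reports can be coded. The downsides are that the TEE claim may become less favourable, a common FQ is itself biased against low-CHO if adherence is good, intake is self-reported, and RQ may be missing for some women.

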After baseline testing, participants were randomized to one of two diets (low-glycemic, LG or high glycemic, HG) using a computer generated randomization scheme prepared with PROC PLAN in SAS Ver. 9.4.

16b Allocation concealment mechanism

Randomizations were placed in sealed sequentially numbered envelopes until interventions were assigned. All participants who give consent for participation, who fulfill the inclusion criteria, and complete baseline testing will be randomized. Participants will be enrolled by eligibility from the study team (principal investigator, coordinators, and dietitians). Study Coordinator will open sequentially numbered envelopes for diet intervention. The study dietitians will reveal the diet intervention to participants, along with a detailed diet introduction and explanation.

17a Blinding (masking)

No blinding. Since it was necessary to reveal the diet assignment to the study dietitian and the participant for appropriate diet introduction and education to the participant, this study will not involve blinding.

17b Blinding (masking): emergency unblinding

N/A

Methods: Data collection, management, and analysis

18a Data collection plan

All measurements will be done in the Core facilities of the Center for Clinical and Translational Science (CCTS), Nutrition Obesity Research Center (NORC), and Diabetes Research Center (DRC) at UAB. Participants will be instructed to avoid strenuous physical

activity (PA) the day prior to testing, and all PA on the morning of testing. All S_I tests will be performed in the Clinical Research Unit (CRU) at UAB's CCTS after an overnight fast of 12 h. The following measurements will be performed at baseline and end of weeks 10 and 14, unless otherwise stated.

S_I will be assessed at baseline only using the intravenous glucose tolerance test (IVGTT) and minimal modeling, as previously described (2), but using 300 mg of glucose (20 % dextrose)/kg of body weight. AIRg will be calculated as the incremental insulin area-under-the-curve from minutes 0–10 following glucose injection using the trapezoidal method.

Body composition (FM and fat-free mass) will be determined by bioimpedance analysis (BIA) (Seca 514 mBCA, Seca GmHb & Co. KG, Hamburg, Germany).

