We will also test for menopausal status as potential predictors of the independent variables of interest, and include this variable in the models if necessary. The primary analyses will treat S_i as a continuous variable and test for independent and interactive effects of S_i and diet in statistical models. For sub-group analyses the median S_i will be used to designate status: high vs low S_i .

20b Statistics: additional analyses

N/A

20c Statistics: analysis population and missing data

N/A

Methods: Monitoring

21a Data monitoring: formal committee

[name] –Professor in the Department of Nutrition Sciences is appointed as the Independent Safety Monitor to provide independent monitoring and review of the protocol every 6 months.

21b Data monitoring: interim analysis

Description of interim analyses and stopping guidelines:

22. Harms

If an individual indicates discomfort or the desire to discontinue testing, tests will be terminated immediately. During routine visits and telephone calls, the study coordinator will query

participants for any adverse events since their last contact with study personnel. In the case of an adverse event during times of testing, a study physician will be on call. The physician will provide medical supervision for this study. All adverse events will be reported to the UAB IRB and reviewed by the investigative team. Should any of these individuals and/or the IRB identify that any adverse event may be related to the study protocol, testing will be suspended, and the protocol will be amended accordingly.

23. Auditing

A progress report will be submitted annually to the sponsor and to UAB IRB.

Ethics and dissemination

24. Research ethics approval

The study is approved by UAB IRB (IRB-300001324) and annual progress reports will be sent to UAB IRB during the full duration of the study.

25. Protocol amendments

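### The FM analysis is restricted to women with week-10 body composition and has no missing-data plan, so selective dropout could distort the diet contrast undetected

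*Combined protocol and SAP*

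**What the plan says.** Section 20a defines the analysis set: "Participants will be included in the analysis if they have S_I data at baseline, and body composition at baseline and week 10". It then fits one generalized linear model, with week-10 FM as outcome and baseline FM, diet and S_I (and/or AIRg) as covariates. A diet × S_I term is added for the moderation hypothesis.

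The sections headed "20b Statistics: additional analyses" and "20c Statistics: analysis population and missing data" both contain only N/A. Section 18b covers retention (weekly contact and reminders), not missing values. Section 14 states no dropout allowance.

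The visit schedule for body composition is not consistent:
- Section 12 gives "body composition with bioimpedance at baseline and Wk10" and adds "REE and body composition will also be measured at week 5".
- Section 18a, which covers bioimpedance (BIA), says "The following measurements will be performed at baseline and end of weeks 10 and 14, unless otherwise stated". That includes week 14 but not week 5.
- Section 11c lists "body weight and composition by bioelectrical Impedance Analysis" as an adherence measure, with no visit time.

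Section 11c also has women telephone weekly to "report current body weight, and troubleshooting/support from a Registered Dietitian", so weekly weights should exist.

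**The concern.** Under section 16a women are randomised after baseline testing. The S_I and baseline FM conditions therefore precede randomisation and do not unbalance the arms. The week-10 condition follows it. A woman lost before week 10 contributes nothing to the FM result, even if her week-5 FM is on file.

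Losing women at random costs only precision. The diet contrast is biased when missingness depends on FM response and one of the following holds:
- (a) the dependence differs by arm, which is possible because diet assignment is open (section 17a);
- (b) the dependence is the same in both arms, but the dropout level differs;
- (c) one rule on absolute FM loss applies to both arms and the diets truly differ, so the arm losing less fat drops out more.

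Cases (a) and (b) can inflate the false-positive rate. Case (c) only shrinks a true difference. Section 14 says FM loss by diet is the comparison that sized the trial, and the plan contains no analysis that would reveal any of the three.

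**Working it through.** **The plan's own figure.** Section 14 states 80% power for 2.5 kg with 37 per arm but gives no SD. I read its low- and high-glycemic labels as low-CHO and low-fat. Three SDs can be derived:
- From the SEMs (1.0 and 0.9), assuming the 17 women split 8/9: √[(7×8×1.0² + 8×9×0.9²)/15] = √(114.32/15) = 2.76 kg. This gives about 97% power, so the stated 80% is not reproduced.
- From P = 0.113 on 15 df: t = 1.683, so SD = 2.5/(1.683 × √(1/8 + 1/9)) = 3.06 kg.
- Solving a two-sided 5% t-test for 80% power at 37 per arm: 3.79 kg.

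The mismatch is a separate matter. I use 2.76 kg and show 3.79 kg as the other end.

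**Assumptions not in the documents.** The week-5/week-10 response correlation is ρ = 0.75. Let z be a woman's week-5 response in SD units around her arm's mean, with higher meaning more FM loss. Then P(missing week 10) = 1/(1 + exp(−a + bz)), with a set to give the chosen dropout rate. At 25% dropout:
- b = 0.25 (weak): 35% dropout at 2 SD poorer response and 17% at 2 SD better;
- b = 0.75 (mild): 57% and 6%;
- b = 1.5 (steep): 81% and 1%.

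**Case (a): 25% response-related loss in low-fat, 20% random loss in low-CHO, true difference 2.5 kg.** The low-fat completers' mean loss is too large by ρ × SD × E[z | observed]. Numerical integration gives E[z | observed] = 0.062, 0.170 and 0.277 for the three slopes. With 0.75 × 2.76 = 2.07:

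| b | Bias, kg | Diet contrast, kg |
|---|---|---|
| 0.25 | 2.07 × 0.062 = 0.13 | 2.37 |
| 0.75 | 2.07 × 0.170 = 0.35 | 2.15 |
| 1.5 | 2.07 × 0.277 = 0.57 | 1.93 |

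Simulated trials fitted with the planned model agree: about 2.38, 2.15 and 1.93 kg. At 10% loss in low-fat, E[z | observed] is 0.071 (mild) and 0.122 (steep), giving about 2.35 and 2.25 kg.

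Simulated power, with the same numbers lost:

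| SD, kg | Random loss | b = 0.75 | b = 1.5 |
|---|---|---|---|
| 2.76 | 90% | 81% | 74% |
| 3.79 | 66% | 50% | 40% |

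With the pattern in low-CHO instead, the contrast rises to 2.86 (mild) and 3.08 kg (steep). If there is no true difference, the false-positive rate is 7.5% (mild) to 12% (steep) at 25%/20% loss. It is about 5.5% at b = 0.25, and about 6% for mild to steep dependence with 10% lost in each arm.

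**Case (b): same slope, 33% loss in low-fat and 13% in low-CHO, no true difference.** E[z | observed] is 0.222 and 0.091 (mild), or 0.357 and 0.154 (steep). The bias is 2.07 × (0.222 − 0.091) = 0.27 kg to 2.07 × (0.357 − 0.154) = 0.42 kg, against low-CHO. The simulated false-positive rate is about 7% to 9%.

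**Case (c): one absolute rule, 25% loss overall, true difference 2.5 kg.** Simulated contrast, mild to steep: 2.34 to 2.15 kg if week-5-related, 2.29 to 2.00 kg if week-10-related. In the week-10-related version dropout is 31%/19% to 34%/16% (low-fat/low-CHO). The false-positive rate stays at 5%.

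**No-bias case.** Steep dependence around each arm's own mean, 25% loss in both arms: 2.50 kg.

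**What week-5 FM recovers.**
- Week-5-related dropout: adding week-5 FM returns 2.5 kg, which the assumption guarantees.
- Week-10-related dropout in low-fat only: the completers' estimate is 2.03 (mild) and 1.72 kg (steep). Adding week-5 FM gives 2.28 and 2.13 kg, so about half the bias goes.
- All dropouts leaving before week 5: no gain. Weekly weights, at an assumed correlation of 0.5 to 0.8 with week-5 response, move 2.15 to between 2.25 and 2.36 kg (mild), and 1.92 to between 2.06 and 2.28 kg (steep).

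**Diet × S_I coefficient.** With no true interaction, the completers' bias is at most 0.23 kg per SD of S_I and the rejection rate is 4% to 7%.

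**The case against.** Harm is not shown. The plan gives no dropout rate and no sign of differential dropout. Food is provided, contact is weekly, and the weight-loss phase lasts only 10 weeks. All of this stands, and dropout may prove too small to matter.

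The primary objective (section 2.1) also covers the interactive effects of S_I, AIRg and diet, and that part is little touched. This stands too, so the point is confined to the diet contrast.

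Replacing the written model may be post hoc: section 13 has enrolment running to August 2023, and parts of section 20a are in the past tense. This stands and shapes the fix. It does not excuse having no sensitivity analysis.

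A reader might infer more than the documents support:
- That a completers' analysis is biased whatever the dropout. It is not when dependence and dropout are equal across arms.
- That requiring S_I breaks the randomisation. It is measured before randomisation.
- That no analysis population is defined. Section 20a defines one; handling of missing data and an all-randomised analysis are what is absent.
- That the COVID amendment made body composition optional. It names only the REE and exercise tests as optional.

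**Conclusion.** The concern holds in conditional form and should be fixed. The completers-only rule, the two N/A sections and the unused week-5 measurement are certain from the text. Whether bias occurs, in which direction and how large it is cannot be determined from the documents.

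Under the assumptions shown, one-sided response-related loss of 25% takes a true 2.5 kg to between 2.4 and 1.9 kg, or, in the other arm, produces false positives at about 7.5% to 12%. At 10% loss the effect is small. These figures illustrate exposure and do not estimate what happened in this trial.

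**What to change.** 1. Reconcile sections 12, 18a and 11c on whether week-5 and week-14 BIA were done.
2. Add to sections 20a and 20c an analysis of all randomised women in their assigned arm: a likelihood-based mixed model for FM at baseline, week 5 and week 10, with diet × time, S_I (and/or AIRg) × time, unstructured covariance and equal baseline means. Report the week-10 diet contrast. Test moderation with diet × S_I × time.
3. If week-5 BIA was not done, impute week-10 FM by arm from baseline FM, S_I, week-14 FM (if measured) and weekly weights.
4. Add a delta-adjusted sensitivity analysis by arm, for example 0 to 3 kg less FM loss in missing women. With 20% to 25% missing in one arm, each 1 kg shifts the contrast by 0.20 to 0.25 kg.
5. Report missing week-5 and week-10 FM by arm and reason.
6. Make the all-randomised model primary only if outcome data have not been analysed, and keep the planned model as a sensitivity analysis. Otherwise keep the planned model and label the new analyses as sensitivity analyses that must be consistent with it before a diet effect is claimed.

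The cost is SAP text and modest analysis work, with no new measurement. The mixed model assumes data are missing at random and adds little precision (SE 0.72 to 0.68 kg with 20% random loss). It corrects only partly when dropout depends on unseen week-10 response or happens before week 5. The weekly weights are self-reported.
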